Appendix I

VAGINAL MORBIDITY AT GYNAECOLOGICAL EXAMINATION

It is advised to manually assess adhesions before inserting the speculum for gynecological examination. In addition to grading, it is mandatory to specify the exact location of toxicity on the provided 3D vaginal map, divided into upper, middle, and lower thirds.

| | |
|---------------------------------------|--|
| Participant ID | |
| Time since last RT | |
| Date | |
| Family status |  no partner  partner |
| Menopausal status |  premenopausal  postmenopausal |
| Smoking status |  Never  Previous  Active |
| WHO performance status |  P0  P1  P2  P3 |
| Specify co-morbidities | |
| Vaginal stricture (CTCAE v. 5) |  None  Asymptomatic; mild vaginal shortening or narrowing  Vaginal narrowing and/or shortening not interfering with physical examination  Vaginal narrowing and/or shortening interfering with the use of tampons, sexual activity, or physical examination |

| | |
|---------------------------|--|
| Vaginal Adhesions | 
 no adhesions
 
 adhesions in the upper third
 
 adhesions in the middle third
 
 adhesions in the lower third
  
Upper third
 
Middle third
 
Lower third
 |
| Vaginal Elasticity | 
 tissue soft and mobile
 
 tissue a little firm and mobile
 
 tissue quite hard with limited mobility
 
 tissue hard and immobile
 
 complete obliteration, not accessible
 |
| Vaginal Fibrosis | 
 no fibrosis
 
 fibrosis in the upper third
 
 fibrosis in the middle third
 
 fibrosis in the lower third
  
Upper third
 
Middle third
 
Lower third
 |

| | | | |
|--|---|--|--------------|
| Vaginal Telangiectasia | 
 no telangiectasia
 
 telangiectasia in the upper third
 
 telangiectasia in the middle third
 
 telangiectasia in the lower third
 | | Upper third |
| Vaginal Telangiectasia contact bleeding | 
 no telangiectasia
 
 TA without contact bleeding
 
 TA with contact bleeding
 | | Middle third |
| Vaginal Fragility / Bleeding with examination | 
 none / robust
 
 development of erythema or petechiae, no surface bleeding
 
 moderate surface fragility with minimal trace bleeding
 
 overt/obvious bleeding with examination
 | | Lower third |
| Vaginal Ulceration | 
 none
 
 limited ($<1\text{cm}^2$) superficial ulceration (loss of surface epithelium)
 
 widespread ($>1\text{cm}^2$) or deep ulceration (loss/devitalisation of deeper tissue layers/necrosis)
 | | Upper third |
| | | | Middle third |
| | | | Lower third |

Appendix 2

| Instrument | Description | Number of Items | Sub-scales | Answer Categories | References |
|-----------------|--|-----------------|---|--|--|
| FSFI | Measures female sexual function across six domains. | 19 | Desire Arousal Lubrication orgasm Satisfaction Pain | 0 (no activity) to 5 (optimal function). | Rosen (2000) ²¹ Wiegel (2005) ²² Meston (2020) ²³ |
| EORTC QLQ-C30 | Core QoL questionnaire for cancer patients in clinical trials. | 30 | Functional (physical, role, emotional, cognitive, social) Symptoms (fatigue, nausea/vomiting, pain) Global health Single items (e.g., insomnia) | 1 to 4 Likert scale (1 to 7 for global health status). | Aaronson(1993) ²⁴ Osoba (1997) ²⁵ |
| EORTC QLQ-ANL27 | Anal cancer-specific QoL module supplementing QLQ-C30. | 27 | Bowel symptoms (with/without stoma) Pain/discomfort Stoma-care Vaginal symptoms Urinary frequency and urgency, swelling in legs, self-cleaning, planning activities, sex life, sexual interest, painful intercourse, and erectile problems. | 1 to 4 Likert scale. | Sodergren (2023) ²⁶ |
| EORTC QLQ-SH22 | Sexual health assessment for cancer patients/survivors. | 22 | Sexual satisfaction Sexual pain Sexual activity, decreased libido, incontinence, fatigue, treatment, communication with professionals, partnership, confidence erection body image (male), body image (female), vaginal dryness | 1 to 4 Likert scale. | Greimel (2021) ²⁷ |

Appendix 3

Pattern of care questionnaire:

| | |
|--|---|
| After your radiotherapy treatment, have you, at any point, performed vaginal dilation, either by using vaginal dilators or through vaginal intercourse? |  No  Yes |
| If No: Why have you not performed vaginal dilation? | ----- |
| If Yes: How often did you perform vaginal dilation during the first 6-12 months after radiotherapy, either by using vaginal dilators or through vaginal intercourse? If you have not reached 12 months after completing radiotherapy, how often have you performed vaginal dilation since radiotherapy, either by using vaginal dilators or through vaginal intercourse? |  Not at all  Less than/or one time per month  1-4 times per month  2-3 times per week or more  Don't remember |
| How often have you performed vaginal dilation in the past 3 months, either by using vaginal dilators or through vaginal intercourse? |  Not at all  Less than/or one time per month  1-4 times per month  2-3 times per week or more  Don't remember |
| If Not at all: When did you stop? And why? | ----- |
| Do you use any hormone therapy? |  No  Lokal hormone treatment (e.g. Vagifem)  Systemic hormone treatment |
| After completing radiotherapy, have you had one or more consultations with specialized sexual health nurses or another sexologist to discuss sexual issues related to your cancer treatment? |  No, I have not had any consultations.  No, but I would have liked to.  Yes, I have had one or more consultations |

Appendix 4

Semi-Structured Interview Guide: Patient Satisfaction with Counseling

Introduction

Welcome

"Thank you for participating. My name is [your name], and I would like to discuss your experiences with guidance regarding gynecological and sexual issues after radiation therapy for anal cancer."

"Your input will help us improve how we support patients in the future. Participation is voluntary, and you can skip questions or end the interview anytime. Your answers will remain confidential."

"Before we begin, do you have any questions for me?"

Section 1: Background information

- Have you experienced any side effects related to gynecological issues or sexual dysfunction, such as localized pain in the vaginal area, vaginal bleeding, narrowing of the vagina, abnormal discharge, or more general effects on sexual function or desire, including impacts on body image?

Section 2: Information received

- **What and When:**

Can you describe what information you were given about gynecological and sexual side effects?

When during your treatment journey were you informed about these potential side effects? And by who?

- **Adequacy of information:**

What do you think about the timing and amount of information on the topic you were given?

Section 3: Preparedness and Support

- **Preparedness:**

Did the guidance you received make you feel adequately prepared to handle these side effects? Why or why not?

- **Barriers:**

Were there any barriers for you to discuss gynecological or sexual issues with healthcare providers?

If yes, what were these barriers (e.g., discomfort, lack of time, cultural factors)?

Section 4: Preferences for Communication

- **Preferred Healthcare Professional:**

Is there a particular type of healthcare professional you feel most comfortable discussing these issues with (e.g., nurse, doctor, counselor)?

- **Suggestions for Improvement:**

Do you have any suggestions on how guidance about these side effects could be improved for future patients?

Conclusion

- **Wrap-Up:**

Is there anything else you would like to share about your experience or the guidance you received?

- **Thank You:**

Thank the participant for their time and valuable insights.

References

2. Camilla Kronborg BMH, [name] Garm Spindler, Eva Serup-Hansen. *Onkologisk behandling af lokaliseret anal cancer*. 2024. <https://dacnet.dk/kliniske-retningslinjer/>

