Another significant challenge is the poorly understood relationship between radiation dose and vaginal toxicity after AC treatment, which complicates the establishment of clinically relevant dose constraints for sexual OARs. While some studies have explored dose-response relationships, findings remain inconsistent. For instance, Arzola et al. (2023)⁹ suggested that keeping the dose to 50% of the anterior vaginal wall <48 Gy could reduce the risks of impaired sexual function. Similarly, Son et al. (2015)¹⁰ proposed that mean vaginal doses below 43 Gy were associated with a reduced risk of severe vaginal stenosis. Conversely, other studies, including Joseph et al. (2016)¹¹, have failed to demonstrate significant correlations between vaginal dose metrics and sexual dysfunction outcomes measured through standardized instruments like the EORTC-CR29.

These discrepancies underscore the urgent need for further research into the mechanisms and clinical predictors of gynecological morbidity and sexual health following CRT. Exploring dose constraints could pave the way for enhanced survivorship care in women treated for anal cancer.

Secondary preventive strategies

Despite well-documented risks, the implementation of secondary preventive strategies for mitigating long-term complications still needs to be revised. Evidence supports that vaginal dilator use and sexual counseling can reduce the risk and severity of late effects following radiation therapy¹²⁻¹⁵. Currently, all Danish cancer treatment centers routinely provide vaginal dilators to female patients after the end of radiation therapy with basic information on their use. The general recommendation

is to initiate dilator use approximately six to eight weeks post-radiation treatment, with a suggested frequency of three times per week.

In Denmark, patients can be referred to specialized sexual health nurses for counseling on sexual dysfunction after treatment for anal cancer. Additionally, all centers have access to late-effects clinics for further support. However, systematic documentation regarding the type and extent of counseling provided is lacking, as is a comprehensive insight into patients' satisfaction with these services. Greater patient involvement in refining guidance and care strategies is crucial to meeting unmet needs and enhancing survivors' quality of life.

Purpose

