The primary objective of this study is to examine the prevalence and severity of vaginal morbidity in women following treatment for localized anal cancer and to identify predictive factors, including the potential dose-response relationship between radiation exposure and morbidity. Furthermore, the study seeks to investigate possible correlations between vaginal morbidity and patient-reported sexual dysfunction.

The secondary objective is to investigate patterns of care related to managing gynecological toxicity and sexual dysfunction, including the use of dilators and hormone therapy. The study also evaluates patient satisfaction with the guidance provided to identify areas for improvement, aiming to support the development of standardized, high-quality practices that ensure consistent and patient-centered care across Denmark's three anal cancer treatment centers.

Study design

This is a national multicenter, cross-sectional study that collects quantitative and qualitative data from gynecological examinations, questionnaires, and semi-structured interviews.

Study population

Inclusion criteria:

- Female patients aged 18 or older.
- Diagnosed with AC and treated with CRT with curative intent.
- 6–36 months post-CRT.
- Willing and able to provide informed consent.

Exclusion criteria:

- History of pelvic radiotherapy for conditions other than the current diagnosis.
- Treatment with electron beam radiotherapy.
- Non-Danish speaking

Inclusion procedures

Participants will be identified during follow-up consultations (6-36 months) at Aarhus University Hospital, Vejle Hospital, and Herlev and Gentofte Hospital. When a potential participant is identified, the treating physician responsible for the consultation will provide both oral and written information about the study. Participants will be informed that they have the right to have a companion or support person present during the initial oral information consultation. To ensure sufficient time for consideration, participants will be offered an inclusion consultation at least 24 hours after the initial

consultation. During this consultation, further questions can be addressed, and participants are welcome to bring a companion or relative.

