Written informed consent will be obtained at this inclusion consultation before study participation. Patients will be assured of confidentiality. Patients will be informed that their participation is entirely voluntary and that they can withdraw their consent at any time without affecting their future care.

If they consent, the gynecological examination will either be performed shortly after consent or scheduled for their next follow-up visit, depending on patient preference and clinical feasibility.

Endpoints

Primary endpoint:

- Prevalence of vaginal stenosis grade 2 or higher.

Secondary endpoints:

- Gynecological findings: vaginal elasticity, adhesions, telangiectasias, ulceration, and bleeding.
- Radiation Dose to sexual organs at risk
- Patient-reported outcomes on sexual health issues
- Pattern of care; dilator use, lubrication, hormone treatment(local/systemic), received specialized sexual counseling.
- Patient satisfaction with the existing sexual rehabilitation program

Data collection

1. Sociodemographic data

Sociodemographic data will be collected via a case report form (CRF) during the consultation where the gynecological examination is performed. This data includes age, smoking status, menopausal status, relationship status, WHO performance status, and comorbidities. (first part of Appendix 1)

2. Clinical data

Clinical data will be extracted from medical records. They will encompass details of the anal cancer diagnosis, including tumor location (with specific information on vaginal invasion if present), tumor volume and length, histological type, and TNM classification. Information about the treatments received will be detailed, including radiation dose and fractionation schedule, as well as chemotherapy regimens. Additionally, data on any salvage surgery or recurrence will be collected, along with details of any subsequent treatments provided for the recurrence. Access to these records will be granted to the principal investigator and relevant regulatory authorities for research purposes, including monitoring, quality control, and compliance with required oversight.

3. Gynecological examinations:

Comprehensive vaginal morbidity will be assessed using an electronic case report form, as detailed in Appendix 1. The morbidity assessment form is based on vaginal morbidity documentation following radiotherapy for cervical cancer, as described by Kirchheiner (2012)¹⁶. This methodology has also been employed in Suval (2023)¹⁷.

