To ensure uniform grading of vaginal morbidity across the study sites, a dedicated seminar will be held before the initiation of patient inclusion. This seminar will involve all relevant physicians responsible for assessments at the three participating centers to align understanding and grading practices, minimize inter-observer variability, and ensure consistency in evaluations throughout the study.

4. Patient-reported outcome measures:

Electronic surveys will be sent following the control visit where the gynecological examination is performed. A reminder email will be sent after one week if a response is missing. If the patient cannot access the survey electronically, it will be handed in on paper form during the consultation and entered electronically afterward.

The survey will include validated questionnaires: the European Organization for the Research and Treatment of Cancer Quality of Life Core Questionnaire (EORTC QLQ-C30) with the Anal Cancer Module (EORTC-QLQ-ANL27), EORTC Sexual Health Questionnaire (EORTC-QLQ-SH22), and Female Sexual Function Index (FSFI). See Appendix 2 for details on these questionnaires.

In addition to the questionnaires mentioned, there will be questions regarding patterns of care, see Appendix 3

5. Radiation Dose parameter:

The principal investigator will retrospectively delineate the vagina on therapy scans from the included participants in accordance with applicable delineation guidelines. Based on this, a retrospective analysis of dose-volume histograms will be performed to identify correlations between vaginal morbidity and radiation exposure.

6. Interviews:

Semi-structured interviews with early participants will be conducted over the telephone using the interview guide provided in Appendix 4. The interviews will be conducted with notes taken on themes and quotes during the sessions for further analysis.

Data management

All data will be entered into a secure electronic database (REDCap) hosted at Aarhus University Hospital. Compliance with GDPR and Danish data protection regulations will be ensured.

Sample size and statistical analysis plan

Sample size

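### Appendix 3 cannot separate dilator use from intercourse and has no item on lubricant use, although dilator use and lubrication are listed as pattern-of-care endpoints

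*Protocol*

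**What the plan says.** The secondary objective (Protocol, Purpose) concerns patterns of care for gynaecological toxicity and sexual dysfunction, "including the use of dilators and hormone therapy". The Secondary endpoints list spells this out as "Pattern of care; dilator use, lubrication, hormone treatment(local/systemic), received specialized sexual counseling". Patient-reported sexual health is a separate bullet in the same list.

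The Data collection section, under patient-reported outcome measures, names the source: besides the validated questionnaires, "there will be questions regarding patterns of care, see Appendix 3".

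Appendix 3 has five closed items: three on dilation, one on hormone therapy and one on counselling. The first dilation item reads "After your radiotherapy treatment, have you, at any point, performed vaginal dilation, either by using vaginal dilators or through vaginal intercourse". The other two ask how often, for the early period after radiotherapy and for the past three months, and repeat the same either-or clause. Two open questions follow: "Why have you not performed vaginal dilation" after a No to the first item, and "When did you stop? And why" after *Not at all* to the three-month item.

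**The concern.** The objective and the endpoint are worded as dilator use, but the items measure dilation by either route. A Yes may mean a dilator, intercourse or both, and no later item asks which.

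The difference matters in this study. The section on secondary preventive strategies states that "all Danish cancer treatment centers routinely provide vaginal dilators to female patients after the end of radiation therapy". Whether women use the device they are given is thus a direct question about care, and the Purpose section aims at consistent practice across three centres. Intercourse is not something a centre provides.

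Lubrication is named as an endpoint component but has no item of its own in the form meant to supply it. Both gaps arise at data collection, so an analysis plan could not repair them afterwards.

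**Working it through.** The Protocol gives no figure to reproduce here. The check sets each endpoint component beside its source.

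| Component (Secondary endpoints) | Appendix 3 | Result |
|---|---|---|
| Dilator use | 3 closed items, all combined with intercourse | Upper bound and non-use only |
| Lubrication | 0 items | No measure of lubricant use |
| Hormone treatment | 1 item (none, local, systemic) | Covered |
| Specialised counselling | 1 item | Covered |

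**Step 1, what the dilation items identify.** A No to the first item, or *Not at all* to a period item, means that the woman used no dilator in that period. A Yes leaves the route open. If *k* of *N* women answer Yes to the first item, the number who ever used a dilator lies between 0 and *k*, so the proportion lies between 0 and *k/N*. As an illustration only, with the planned *N* = 80 and an assumed *k* = 40, the range is 0/80 = 0% to 40/80 = 50%. The value of *k* is not in the Protocol; the conclusion does not depend on it.

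**Step 2, the reasons.** Both reason questions (2 of 2) open only after a combined negative. A woman who has intercourse but never used a dilator answers Yes and is not asked why. One who gave up the dilator but has had intercourse in the past three months does not tick *Not at all*, and is not asked why she stopped. Free text may reveal the route for some of the women who are asked.

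**Step 3, other sources for dilator use.** The examination form (Appendix I), the listed sociodemographic and medical-record data and the interview guide (Appendix 4) do not ask about it. Appendix 2 indicates that the FSFI has a no-activity answer and that the SH22 covers sexual activity. Cross-reading these could show that some Yes answers from sexually inactive women must mean dilators. The Protocol does not plan this, gives no recall period that would match those answers to any of the three items, and could not separate the routes in sexually active women, who may also use dilators.

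**Step 4, sources for lubrication.** The FSFI has a lubrication domain and the SH22 a vaginal dryness item. As Appendix 2 describes them, the first measures sexual function and the second a symptom. Neither is described as recording use of a product. Only scale names are shown, so this holds for the instruments as the Protocol describes them.

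**The case against.** **The combination may be deliberate.** The either-or clause appears four times in Appendix 3, including the alternative wording for women not yet at 12 months. The title of reference 15, cited in support of dilators, names regular dilator use and/or sexual activity as its exposure. This stands as far as it goes: if combined dilation is the intended variable, the fault on that limb lies in the wording of the objective and endpoint, and relabelling would cure it. It would still give no figure for dilator use.

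**Lubrication may mean the FSFI domain.** The endpoint does not say lubricant, and the secondary objective does not mention lubrication. Reading it as lubricant use is an inference, drawn from its place under pattern of care between dilator use and hormone treatment, while sexual health outcomes have their own bullet. I think it the more natural reading, but the sponsor should confirm it.

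**The form is not useless.** A reader might infer that dilator use has no usable measure at all. That goes too far: non-use by women who did neither is identified, and the share and frequency of any dilation are measured.

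**It is one descriptive endpoint among five secondary ones.** True, and the grading should reflect that. A reader might also infer that the stenosis prevalence or the dose-response analysis is compromised. The Protocol does not support this: neither analysis, as described, uses the pattern-of-care items.

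**Conclusion.** The point holds in a limited form. Of four pattern-of-care components, two are affected. All three closed dilation items and both reason questions combine dilators with intercourse, and no item asks about lubricant use. The plan, followed exactly, can report any dilation, women who did neither, and an upper bound on dilator use. It cannot report the prevalence or frequency of dilator use among sexually active women, or their reasons for not using or stopping.

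The dilator limb rests on the wording of the objective, endpoint and items alone. The lubrication limb also rests on reading the word as lubricant use and on the questionnaires being as Appendix 2 describes them. This should be changed, but it concerns a descriptive secondary endpoint; the primary endpoint and the sample size are unaffected.

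**What to change.** In Appendix 3:

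1. Ask dilator use and intercourse as separate items, each with its own frequency. Combined ever-use then follows exactly, and combined frequency to within the answer bands.
2. Attach the questions on not starting and on stopping to the dilator item.
3. Add one item on lubricant or moisturiser use.

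If combined dilation is what the study wants, relabel it so in the Purpose and Secondary endpoints sections, and either add the lubricant item or remove or redefine lubrication.

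The cost is at most 3 (split items) + 1 (lubricant) = 4 closed items on top of the present five, fewer with skips. No validated instrument is touched. A protocol amendment with ethics approval may be needed.

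Inclusion is tentatively 01.05.2025 to 01.05.2026, so a change during that period reaches only some women directly. Since "Electronic surveys will be sent following the control visit where the gynecological examination is performed", earlier responders could receive a short electronic supplement, at the price of a second contact on a sensitive subject. Its past-three-months window would differ from the one at their examination. So send them only the ever-use and early-period items, or report them separately as combined dilation. If collection has closed, report combined dilation under that name and state that lubricant use was not collected.
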